### **Approach**

**The aim of this project is to conduct a pilot study to investigate the feasibility and initial efficacy of applying FE to individuals with MS to improve motor function, cognitive function, and QOL.**

**Experimental Overview:** A pilot study is proposed in which 20 individuals with MS presenting with an Expanded Disability Status Scale score between 2.0 and 6.5 will be eligible to participate. Participants will be screened using the American College of Sports Medicine Exercise Preparticipation Health Screening algorithm. The potential participant's physician will be notified of the study protocol and their patient's desire to participate. Eligible participants will undergo clinical and biomechanical assessments evaluating lower extremity function, processing speed, memory, and self-reported quality of life at baseline and post-intervention. Following baseline testing, participants will be randomized to undergo FE (n=10) or VE (n=10). Randomization will be stratified based on EDSS level (2.0-4.0 vs. 4.5-6.5) to facilitate comparable levels of disability in both groups. Participants in both groups will attend exercise sessions twice a week for 12 weeks. The FE intervention will consist of forced-rate aerobic exercise on a stationary semi-recumbent bicycle. Target cadence will be 80 revolutions per minute (RPM). Should the participant not tolerate the 80 RPM cadence, a self-selected cadence will be used initially, and increased by 5 RPM each session until the target cadence of 80 RPM is achieved. The VE intervention will be identical to FE, except participants will cycle at a self-selected cadence on a semi-recumbent stationary cycle ergometer without assistance from the motor. Aerobic intensity for both groups will be monitored continuously throughout the exercise using a heart rate chest strap. Target heart rate will be prescribed at 60-80% of the individual's age-predicted maximum. Following a 5-minute

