warm-up, participants will complete a 35-minute main exercise set with the goal of maintaining their heart rate within the prescribed target zone. A 5-minute cool-down will occur immediately at the end of the 35-minute main exercise set. For the FE group, the cadence during warm up and cool down will be 15-20% less than the target cadence for the main exercise set (80 RPM) during the main exercise set. Water will be provided to the participant ad libitum, but all will be encouraged to drink 16-24 ounces during the exercise session. Cooling vests will be available to participants to avoid overheating as indicated. Rest breaks will be provided as requested, but all participants will be encouraged to progress to an entire 45-minute session without rest breaks.

**Recruitment and Sample:** Physicians and advance practice clinicians within the Mellen Center who would otherwise prescribe physical therapy to their patients will provide prospective participants with a study brochure. Should they express interest in learning more about the study, the study coordinator will call them to follow up. The study team may use MyChart as a way to contact eligible patients with an IRB approved flyer and/or brochure. Twenty-four patients will be recruited for this pilot feasibility study.

**Aim 1: To determine the feasibility of applying FE or VE training to individuals with MS.** Primary outcomes to determine feasibility will include measures of exercise compliance (percent of sessions attended, time spent exercising, time spent within target heart rate zone) and the absence of adverse events. The secondary outcomes will include change in levels fatigue and physical activity.

**Hypothesis 1:** Participants will comply with the FE or VE intervention (exercise frequency, time, and intensity) at  $\geq 90\%$  of the prescribed values and will present with no worsening fatigue or levels of sedentary activity following the FE or VE intervention.

**Aim 2: To determine the effects of a 12-week FE or VE intervention on motor function.** The primary outcome is change in biomechanical characteristics of gait. Secondary outcomes include changes in walking capacity, balance, manual dexterity test (MDT), and timed up and go (iTUG).

**Hypothesis 2:** Improvements in gait biomechanics and walking capacity will be observed following the 12-week FE intervention.

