### **Data Variables**

**Exercise Training Variables:** Overall time, active exercise time, heart rate, cadence, and power are recorded in a secure, customized REDCap database. The primary training variables of interest for each exercise session are: AE intensity measured as percent heart rate reserve (%HRR) during main 35-minute exercise set, average cadence and work (power) produced by the patient and for the FE participants, by the motor.

**Measures of Feasibility (Aim 1):** Primary outcomes to determine feasibility will include measures of exercise compliance (percent of sessions attended, time spent exercising, time spent within target heart rate zone) and the absence of adverse events. Secondary outcomes will include change in levels fatigue and physical activity as measured by a body-worn activity monitor.

**Effects on Motor Function (Aim 2):** The primary outcome is change in biomechanical characteristics of gait, while the secondary outcomes include changes in walking capacity, manual dexterity test (MDT), and timed up and go (iTUG).

**Effects on Non-Motor Function (Aim 3):** The primary outcome measuring QOL is the change in the PROMIS-29, while the MSPT CVLT, and BVMT will serve as the primary outcomes measuring cognitive function.

**Role of Klotho (Aim 4):** The primary outcome is the acute and long-term change in serum Klotho levels from baseline to the post-exercise intervention, while the secondary outcome in long-term change in sNfL

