### **Outcomes:**

**Analysis of Feasibility (Aim 1):** Measures of compliance will determine feasibility of individuals with MS to complete the FE intervention. Self-reported fatigue will be measured using the Modified Fatigue Impact Scale. Activity levels will be measured using a Garmin Vivofit 4 body-worn activity monitor. The absence of adverse events will demonstrate safety of FE in MS.

**Biomechanical Gait Assessment (Aim 2):** The CAREN system is a complete biomechanical assessment system with 10 Vicon cameras, split-belt treadmill with two force plates, and D-flow software. Twenty-five retro-reflective markers will be placed at anatomic landmarks identified for LE assessment. Participants will walk at a self-selected pace for two 2-minute trials. The following biomechanical outcomes will be calculated: 1) spatio-temporal: velocity; cadence, step length, percentage of gait cycle spent in swing and stance phase, single and double limb support time and percentage; 2) Kinematic: hip and knee flexion and extension; ankle dorsi- and plantar-flexion; pelvic obliquity, rotation and tilt. To determine changes in overground walking, gait analysis will also be conducted using the Zeno Instrumented walkway. Participants will walk at a self-selected pace and fast pace for four lengths for each condition along the 15' Zeno Instrumented walkway. The following spatio-temporal outcomes will be calculated: velocity; cadence, step length, percentage of gait cycle spent in swing and stance phase, single and double limb support time and percentage. Lastly, the Timed up and Go will be administered.

**Non-Motor Function Data (Aim 3):** The PROMIS-29 will be administered to determine self-reported quality of life. The multiple sclerosis performance test (MSPT) and two measures of episodic memory, the California Verbal Learning Test and the Brief Visuospatial Memory Test, will be administered to examine change in cognitive function. All will be administered to determine feasibility with respect to administration approach, sensitivity to detect change over time, and time requirements for a future clinical trial.

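### Aim 2 names no deciding gait variable or deciding test: its primary outcome is a domain of about 15 to 27 distinct tests with no multiplicity rule

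*Protocol*

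**What the plan says.** The overall aim in the protocol's Approach section is a pilot "to investigate the feasibility and initial efficacy of applying FE to individuals with MS to improve motor function". For Aim 2, the same section says "The primary outcome is change in biomechanical characteristics of gait", and Data Variables repeats that definition. Neither place picks a variable, device or pace. Hypothesis 2 reads "Improvements in gait biomechanics and walking capacity will be observed following the 12-week FE intervention". Walking capacity is a secondary outcome, and no measure of it is given.

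Under Outcomes, Biomechanical Gait Assessment (Aim 2), the treadmill system yields two lists:

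- spatio-temporal: "velocity; cadence, step length, percentage of gait cycle spent in swing and stance phase, single and double limb support time and percentage"
- kinematic: "hip and knee flexion and extension; ankle dorsi- and plantar-flexion; pelvic obliquity, rotation and tilt"

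The same section adds a second system: "To determine changes in overground walking, gait analysis will also be conducted using the Zeno Instrumented walkway". There, "Participants will walk at a self-selected pace and fast pace for four lengths for each condition", and the spatio-temporal list is calculated again.

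The SAP (Statistical Methods) applies paired t-tests to baseline-to-end change in all motor and non-motor functions, and baseline-adjusted linear regressions to compare the groups on outcomes in general. It refers to two baseline assessments but does not say which one change is measured from. Its only decision rule is the 0.05 threshold.

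**The concern.** A primary outcome should let a reader say, before the data are seen, what result would support the hypothesis. Here the variable, the measuring system, the walking pace and the contrast (change within FE, or FE against VE) are all open. Every gait variable can be tested at 0.05, and nothing says whether one significant improvement among many supports Hypothesis 2. A claim of initial efficacy could then rest on the best of many looks, and a later trial could be planned around a chance finding. Aim 2 is not marked as exploratory; only Aim 4 is.

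**Working it through.** The documents give no power calculation, error rate or test count, so there is no stated figure to reproduce.

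**Count of listed variables** (Outcomes, Aim 2)

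- Treadmill: 9 spatio-temporal + 9 kinematic = 18.
- Walkway: 9 × 2 paces = 18.
- Total: 36.

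**Removal of variables tied by definition.** Averaged over limbs, within one walking condition:

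- velocity = cadence × step length
- stance% = 100 − swing%
- single-support% = swing%
- double-support% = 100 − 2 × swing%
- support time = support% × 120/cadence (percentage as a fraction)

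The four percentages are linear in one another and share one p-value, so 9 variables give 9 − 3 = 6 distinct tests, resting on 3 free quantities.

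- Treadmill: 6 + 9 = 15 tests on 3 + 9 = 12 free quantities.
- All: 3 × 6 + 9 = 27 tests on 3 × 3 + 9 = 18 free quantities.

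This is for one type of analysis. Running both SAP analyses doubles it to 30 to 54 p-values.

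**Chance of a false improvement.** Inputs from the documents: 10 per arm (Approach) and a 0.05 threshold (SAP). Assumptions:

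- two-sided tests, with only the improving direction counted, because Hypothesis 2 predicts improvement
- paired tests within FE
- equal correlation among the free quantities, aligned with improvement
- within-person SDs of 4% (cadence), 5% (step length) and 8% (double-support%)
- improving directions: velocity, cadence, step length, swing% and single-support time up; double support down; one direction for each kinematic variable

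One pre-named variable: 0.05/2 = 2.5%.

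Chance of at least one significant improvement when nothing has changed, n=10, 20,000 simulated trials per case:

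| Correlation | 0 | 0.3 | 0.5 | 0.7 | 0.9 |
|---|---|---|---|---|---|
| All, 27 tests | 43.5% | 34.6% | 28.7% | 22.4% | 15.2% |
| Treadmill, 15 tests | 29.6% | 23.4% | 19.7% | 15.3% | 10.0% |
| All, single-support time left out | 39.9% | 29.5% | 22.9% | 15.9% | 8.4% |
| Treadmill, single-support time left out | 28.0% | 21.5% | 17.6% | 12.9% | 7.5% |

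The last two rows are shown because the improving direction of single-support time is unclear.

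Plausibility check at correlation 0: the 18 independent free quantities alone give 1 − 0.975^18 = 36.6%, and 27 fully independent tests would give 1 − 0.975^27 = 49.5%. The simulated 43.5% lies between them.

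**Sensitivity (27 tests)**

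- n=12 (24 recruited, 24/2 per arm): 43.6% down to 15.0%. n=20 (arms pooled): 43.4% down to 15.0%. Neither moves any entry by more than about 2 points.
- Improving directions not aligned with the correlation: 44.3% down to 19.6%.
- Four other SD choices: 42% to 44% at correlation 0, and 27% to 29% at 0.5.

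**Does naming only the test help?** With the baseline-adjusted regression, 10 per arm and no variable named, the chance of at least one significant FE advantage is 44.1% down to 21.5% (all) and 29.6% down to 14.1% (treadmill), assuming between-person differences independent across variables. The variable must be named too.

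**Detectable effect with one variable and one test** (80% power, two-sided 0.05, noncentral t)

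- Paired, n=10: df = 9, noncentrality d√10; d = 0.996 SD of change.
- Regression, 10 per arm: df = 20 − 3 = 17, noncentrality d/√(1/10 + 1/10); d = 1.33 residual SDs.
- If all tests were kept with Bonferroni (0.05/15 = 0.0033; 0.05/27 = 0.0019), the paired n=10 figure rises from about 1.0 to 1.58 or 1.71.

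**The case against.** The strongest reply is that the any-one-variable rule behind these percentages is not in the documents either. Hypothesis 2 speaks of improvements, in the plural, and joins gait with walking capacity. If one pre-named walking-capacity test also had to improve, the joint false-positive chance could not exceed 2.5%. It is fair that the percentages illustrate what the silence permits and not what the plan prescribes. But no walking-capacity measure and no joint rule is stated, so that protection does not exist as written.

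Second, the SAP does name tests, and it does not say whether the paired tests are run per arm or pooled. Both are true. What is missing is which test decides Aim 2, and pooling hardly changes the figures.

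Third, the count and the sizes depend on assumptions. Merging the paired kinematic directions would leave 12 to 24 distinct tests, and the percentages run from 7.5% to about 44%. The inflation is secure; its exact size is not.

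Fourth, this is a pilot with feasibility as Aim 1, and strict error control is not essential. That stands and sets the priority. It does not remove the point, because the stated aim includes initial efficacy, Aim 2 has a primary outcome and a directional hypothesis, and the SAP declares significance at 0.05 without calling its p-values descriptive.

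**Conclusion.** The concern holds. Aim 2 lacks a deciding variable, a deciding contrast and any rule for many tests. Under a true null, the chance of at least one significant gait improvement is about 15% to 43% for all variables and 10% to 30% for the treadmill alone. Even the most favourable case examined, 7.5%, is three times the 2.5% of one pre-named variable (7.5/2.5 = 3). These sizes rest on assumed correlations, variances and improving directions, and on reading one significant variable as support. The gap in the plan does not depend on them. It should be corrected as a cheap improvement; it does not undermine the pilot.

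**What to change.** Amend the protocol and SAP before analysis:

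1. Name one already-collected gait variable (system, pace, and limb or limb average), or one pre-defined composite, as the Aim 2 primary outcome, with its improving direction.
2. Name one deciding test and which of the two baselines it uses. If the claim is an effect of FE relative to VE, use the SAP's baseline-adjusted regression. If the within-FE paired test is kept because it matches Hypothesis 2, state that it shows change after FE and cannot separate an FE effect from practice or repeat testing.
3. Report the other gait variables as exploratory, with estimates and 95% confidence intervals and no claims of significance.
4. Limit the Hypothesis 2 claim to gait unless a walking-capacity measure and a joint rule are also named.

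If the team cannot choose a variable, declaring all Aim 2 p-values descriptive would also close the gap, but Hypothesis 2 would then not be formally tested.

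The cost is wording only, with no new data. The other gait variables could no longer support Hypothesis 2 on their own, and the single test would have 80% power only for a change of about 1.0 SD (paired) or a difference of about 1.3 residual SDs (regression).

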## Pilot Study Methodology

**Screening:** Individuals ages 18-75 with MS presenting with an Expanded Disability Status Scale score between 2.0 and 6.5 will be eligible to participate. Participants will be screened using the American College of Sports Medicine (ACMS) Exercise Preparticipation Health Screening algorithm. The potential participant's physician will be notified of the study protocol and their patient's desire to participate.

**Forced Aerobic Exercise (FE) and Voluntary Aerobic Exercise (VE) Interventions:** Individuals will participate in a supervised exercise protocol on a stationary semi-recumbent cycle ergometer, comprised of 45-minute sessions. Target heart rate ( $HR_{target}$ ) zone for each subject, based on ACSM recommendations, will be determined based on age- and sex-based norms. All participants will be instructed to exercise within their  $HR_{target}$  during the 35-minute main exercise set, occurring between a 5-minute warm-up and cool-down phase. Those randomized to the FE group will be administered the high-rate AE protocol based on methodology used

in our previous studies on a custom-engineered cycle that augments cycling cadence. Those randomized to the VE group will exercise at their self-selected cadence without assistance from the motor. As in our previous studies, if any patient exhibits signs of cardiac distress or hemodynamic compromise, the session will be stopped immediately, and the on-call physician will be paged to the laboratory. All training will be under the supervision of a physical therapist, exercise physiologist, or medical student certified in Basic Cardiac Life Support.

### **Data Variables**

**Exercise Training Variables:** Overall time, active exercise time, heart rate, cadence, and power are recorded in a secure, customized REDCap database. The primary training variables of interest for each exercise session are: AE intensity measured as percent heart rate reserve (%HRR) during main 35-minute exercise set, average cadence and work (power) produced by the patient and for the FE participants, by the motor.

**Measures of Feasibility (Aim 1):** Primary outcomes to determine feasibility will include measures of exercise compliance (percent of sessions attended, time spent exercising, time spent within target heart rate zone) and the absence of adverse events. Secondary outcomes will include change in levels fatigue and physical activity as measured by a body-worn activity monitor.

**Effects on Motor Function (Aim 2):** The primary outcome is change in biomechanical characteristics of gait, while the secondary outcomes include changes in walking capacity, manual dexterity test (MDT), and timed up and go (iTUG).

**Effects on Non-Motor Function (Aim 3):** The primary outcome measuring QOL is the change in the PROMIS-29, while the MSPT CVLT, and BVMT will serve as the primary outcomes measuring cognitive function.

**Role of Klotho (Aim 4):** The primary outcome is the acute and long-term change in serum Klotho levels from baseline to the post-exercise intervention, while the secondary outcome in long-term change in sNfL

### **Outcomes:**

**Analysis of Feasibility (Aim 1):** Measures of compliance will determine feasibility of individuals with MS to complete the FE intervention. Self-reported fatigue will be measured using the Modified Fatigue Impact Scale. Activity levels will be measured using a Garmin Vivofit 4 body-worn activity monitor. The absence of adverse events will demonstrate safety of FE in MS.

**Biomechanical Gait Assessment (Aim 2):** The CAREN system is a complete biomechanical assessment system with 10 Vicon cameras, split-belt treadmill with two force plates, and D-flow software. Twenty-five retro-reflective markers will be placed at anatomic landmarks identified for LE assessment. Participants will walk at a self-selected pace for two 2-minute trials. The following biomechanical outcomes will be calculated: 1) spatio-temporal: velocity; cadence, step length, percentage of gait cycle spent in swing and stance phase, single and double limb support time and percentage; 2) Kinematic: hip and knee flexion and extension; ankle dorsi- and plantar-flexion; pelvic obliquity, rotation and tilt. To determine changes in overground walking, gait analysis will also be conducted using the Zeno Instrumented walkway. Participants will walk at a self-selected pace and fast pace for four lengths for each condition along the 15' Zeno Instrumented walkway. The following spatio-temporal outcomes will be calculated: velocity; cadence, step length, percentage of gait cycle spent in swing and stance phase, single and double limb support time and percentage. Lastly, the Timed up and Go will be administered.

**Non-Motor Function Data (Aim 3):** The PROMIS-29 will be administered to determine self-reported quality of life. The multiple sclerosis performance test (MSPT) and two measures of episodic memory, the California Verbal Learning Test and the Brief Visuospatial Memory Test, will be administered to examine change in cognitive function. All will be administered to determine feasibility with respect to administration approach, sensitivity to detect change over time, and time requirements for a future clinical trial.

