The Therapeutic Effects of Forced Aerobic Exercise in Multiple Sclerosis

Statistical Analysis

NCT Number: 04906057

Document Date: 07/15/2021

Section of Biostatistics
Quantitative Health Sciences/ JJN-3
[name]

IRB 19-1003: Feasibility study investigating forced and voluntary rate aerobic cycling in persons with multiple sclerosis

Statistical Methods:

Demographics, patient characteristics and exercise parameters will be summarized by mean with standard deviation or median with interquartile range for continuous variables, and count with percentage for categorical variables. Patients will be stratified by exercise groups (FE vs VE).

Changes in motor and non-motor functions from baseline to end of treatment will be examined by paired sample t-tests.

Changes in Klotho level from pre- to post-exercise will be examined by paired sample t-tests, at both first exercise session and last exercise session. Changes in Klotho level from first exercise session to last exercise session will also be examined by paired sample t-tests, at both pre-exercise and post-exercise. Mixed-effect model will be used to examine if there is significant acute change (from pre- to post-exercise) or long-term change (from first to last exercise session) in Klotho level. Patient random effect and exercise group indicator (FE vs VE) will be included in the model. Changes in Neurofilament light (NFL) from baseline to end of treatment will be examined by paired sample t-test.

Effects of exercise parameters on walking outcomes at end of treatment will be examined by linear regressions. Exercise parameters will be in separate models and baseline values of walking outcomes will be adjusted for in the models.

Outcomes measured at end of treatment will be compared between groups using linear regressions. Baseline values of outcomes will be adjusted for in the models.

Changes in exercise parameters over sessions will be examined by mixed-effect models, where session is the independent variable. Patient random effect will be included in the model. Group difference in changes in exercise cadence over sessions will be examined by mixed-effect models, where independent variables include session, group and interaction between session and group. Patient random effect will be included in the model.

We will also compare variables (motor and non-motor functions) between baseline1 and baseline2 using paired sample t-tests.

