P<0.05 will be considered as statistically significant.

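### Zero adverse events in 10 forced-exercise patients cannot demonstrate safety (exact 95% upper limit 30.8%), and the SAP plans no adverse-event analysis

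*Protocol*

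**What the plan says.** The protocol, under Outcomes, Analysis of Feasibility (Aim 1), draws the safety conclusion in advance and without qualification: "The absence of adverse events will demonstrate safety of FE in MS". Freedom from adverse events is listed with the compliance measures as a primary feasibility outcome, both in the Aim 1 statement (Approach) and under Data Variables, Measures of Feasibility. In neither place is it restricted by seriousness or by relation to exercise, and no consequence is attached to a single event.

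On numbers, the Experimental Overview plans 10 FE and 10 voluntary-exercise (VE) patients, while Recruitment and Sample says "Twenty-four patients will be recruited for this pilot feasibility study". On exposure, "Participants in both groups will attend exercise sessions twice a week for 12 weeks".

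In the SAP, the descriptive summaries are limited to three groups of variables: "Demographics, patient characteristics and exercise parameters will be summarized by mean with standard deviation or median with interquartile range" for continuous variables, with counts and percentages for categorical ones. The remaining text covers motor and non-motor function, Klotho, neurofilament light, walking outcomes and exercise parameters. Adverse events are not mentioned.

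**The concern.** The sentence treats the absence of an observation as evidence of the absence of risk. With about ten patients exposed to FE, a clean record is a likely result even when the risk is appreciable. Followed as written, the plan would turn a zero count into a claim of demonstrated safety that the data cannot bear.

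The criterion is also hard to use in the other direction. Any event of any kind breaks it, so one trivial complaint and one serious event count the same. The documents do not say what either would mean for the conclusion.

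The SAP offers no correction. A primary Aim 1 outcome has no planned denominator, summary by arm, classification or interval. The general statement that end-of-treatment outcomes will be compared by linear regression adjusted for baseline does not fit an event count with no baseline value.

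**Working it through.** The documents give no tolerable event rate, no confidence level for safety and no justification of sample size on this outcome, so there is no planned figure to reproduce. The check asks what zero events would establish.

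**Inputs**
- FE patients: n = 10 (Experimental Overview). As a sensitivity case, n = 24/2 = 12, assuming the 24 under Recruitment and Sample are randomised equally.
- Confidence level: 95%, assumed here as the usual choice alongside the SAP's only threshold, "P<0.05 will be considered as statistically significant".
- True per-patient risk of an event over the programme: not in the documents, so a range is shown.

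**Upper limit after zero events.** The exact (Clopper-Pearson) limit for 0 of n is 1 − 0.025^(1/n) two-sided and 1 − 0.05^(1/n) one-sided.

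| FE patients | Two-sided 95% | One-sided 95% |
|---|---|---|
| 10 | 1 − 0.025^(1/10) = 30.8% | 1 − 0.05^(1/10) = 25.9% |
| 12 | 1 − 0.025^(1/12) = 26.5% | 1 − 0.05^(1/12) = 22.1% |

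Pooling both arms would not answer a claim about FE, and it still leaves two-sided limits of 16.8% (0 of 20) or 14.2% (0 of 24).

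**Chance of a clean record.** With true risk p, the probability of no event is (1 − p)^n. This needs no confidence level.

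| True risk p | No event in 10 | No event in 12 | At least one in 10 |
|---|---|---|---|
| 2% | 82% | – | 18% |
| 5% | 60% | 54% | 40% |
| 10% | 35% | 28% | 65% |
| 20% | 11% | 7% | 89% |
| 25% | 6% | 3% | 94% |

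For example, 0.90^10 = 0.349 and 0.80^10 = 0.107. The last column is one minus the second.

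**Counting sessions instead of patients does not help.** Twice weekly for 12 weeks is 24 sessions per patient, or 240 in the FE arm with full attendance. Zero events in 240 gives a per-session limit of 1 − 0.025^(1/240) = 1.53%. Over one patient's 24 sessions that accumulates to 1 − 0.025^(24/240) = 1 − 0.025^(1/10) = 30.8%. This is the same limit, and it relies on sessions within a patient being independent.

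**For scale only.** A two-sided limit below 10% needs ln(0.025)/ln(0.90) = 35.01, so 36 event-free patients. Below 5% it needs ln(0.025)/ln(0.95) = 71.9, so 72. These ceilings are illustrations and are not targets taken from the documents.

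**The case against.** The best defence is context. This is a pilot of feasibility and initial efficacy that looks ahead to a later trial. Hypothesis 1 concerns compliance, fatigue and sedentary activity and does not mention adverse events, and no sample size or go/no-go rule rests on the safety sentence. The protocol also provides preparticipation screening, physician notification, supervised sessions and a procedure for stopping a session. All of this is true, and it limits the weight of the point. It does not alter the sentence or supply an analysis: screening and supervision are conduct measures, and they do not estimate risk.

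A second objection is that 30.8% is hard to read as a safety figure, because it applies to whatever counts as an adverse event. For any event, however minor, such a limit says little about important harm. That is fair, and it is a reason to classify events. If the count is confined to serious or exercise-related events, the same limit applies to a zero count of those, and it then matters more.

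Third, if minor events are common over 12 weeks, a zero count is unlikely and the practical gap is how a non-zero count will be handled. This also stands: the plan overstates one result and leaves the other undefined.

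Finally, the 95% level and the exact method are a reviewer's choice, and a plain descriptive listing could be acceptable in a pilot. A listing would fill the gap in the SAP, but without an interval the reader would not see how little a zero count excludes.

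**Conclusion.** The point holds. Zero events among 10 FE patients would leave per-patient risks up to 30.8% (two-sided 95%) compatible with the data, or 26.5% with 12 patients, so safety would not have been demonstrated. The conclusion is the same for either sample size and for one- or two-sided limits. The figures assume that every FE patient is followed for events throughout and that patients are independent; losses to follow-up would widen the limits. The small sample is reasonable for a pilot. The faults are the unqualified inference and the lack of any planned adverse-event analysis for a primary Aim 1 outcome. They do not invalidate the trial, but they affect what it may conclude and should be corrected.

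**What to change.** Remove the claim that safety will be demonstrated, and put the following in both the protocol and the SAP:

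> The number and proportion of patients with any, serious, and exercise-related adverse events will be reported by arm, with exact 95% confidence intervals based on the observed count and denominator. Results will be described as preliminary safety data.

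Define serious and exercise-related before the data are reviewed.

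The cost is a change of wording in two documents, classification of each event by seriousness and relation to exercise, and one short table. No additional patients are needed. The price to the sponsor is a less favourable safety statement.
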